14.1.2 Capsular Contracture

For the secondary objectives, the incidence of moderate and severe capsular contracture will be examined using proportions of patients who developed Baker grade <II and \geq II capsular contracture, respectively, at 12 or 18 months and 24 or 30 months after IMRT was administered. Incidence of minor revisional surgeries by plastic surgeon will be evaluated by proportions too. Again, the rates (proportions) will be compared across the two groups.

To evaluate cosmesis, the Breast-Q[®] will be utilized in these assessments and will be presented descriptively, giving summary statistics for changes in the Breast-Q[®] scores over time.

Post-treatment MRI outcome is defined as a continuous variable. We will examine the correlation between the 12-month MRI and 12-month Baker score (<II vs \geq II in Group 1 and between the 18-month MRI and 18-month Baker's score in Group 2. The correlation will be assessed by Wilcoxon rank sum tests. We will also examine the sensitivity and specificity of MRI by using Baker score as the gold standard. All patients enrolled will be used for the analysis of secondary objectives if they provided eligible measurements. Analyses for secondary objectives will be done separately for the two groups.

14.1.3 $^{13}\text{N-NH}_3$ PET/CT Feasibility Endpoint

We will assess the feasibility of performing $^{13}\text{N-NH}_3$ PET studies in breast cancer patients undergoing IMRT within the RT simulation session. This involves delivering the dose on time (taking into account the short half life of $^{13}\text{N-NH}_3$), performing all scans successfully, and most importantly, having the patient tolerate all imaging sessions while in the treatment position.

For each patient, if even one out of the two planned studies are unable to generate doses for the heart segments, this patient will be considered as a —failure— towards the endpoint of feasibility. The approach will be declared feasible if we are able to obtain doses for all 17 segments of heart in at least 7 out of 10 patients. Should a patient drop out before they receive their follow-up scan, they will be replaced by another patient, unless the first scan was already a —failure—. We expect n=10 patients, but have budgeted enough scans for 12 patients, in the event a patient gets lost to follow-up/dies and cannot have the second scan, or declines the second scan. However, the decision rule is built by using the first 10 evaluable patients. This decision rule has the following probabilities of declaring success/feasibility.

True feasibility rate	0.85	0.80	0.70	0.60	0.50	0.45
Prob. of declaring feasible	95%	88%	65%	38%	17%	10%

We will further assess feasibility by correlating pre and post-IMRT measures of MBF/CFR with corresponding RT dose delivered to the ventricular myocardium on a global regional and segmental basis. The post-RT studies will help determine the incidence of MBF/CFR changes following radiation as determined by $^{13}\text{N-NH}_3$ PET imaging.

We will measure the correlation between the changes in flow and flow reserve and the dose level in 17 pairs (17 segments per PET data and 17 doses delivered by IMRT). Data will be visually examined first in order to choose the most appropriate correlation coefficient (e.g., Pearson or Spearman or Kendall's Tau, etc., though at this stage we expect that the nonparametric Spearman correlation coefficient will be used). Each patient will thus provide a correlation coefficient. The 10 correlation coefficients for 10 patients in the study will be summarized and descriptive statistics will be computed.

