2.2 Secondary Objectives

- To quantify the incidence of moderate to severe capsular contracture
- To quantify the rates of minor revisional surgeries
- To evaluate cosmesis
- To quantify post-radiation volumetric and capsular changes on MRI and correlate these changes with clinical assessments of capsular contracture.

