9.3 Assessment of Secondary Objectives

9.3.1 Capsular Contracture

Two methods will be employed to assess capsular contracture. These include the current standard assessment tool, the Modified Baker score, and MRI. All follow-up assessments will be compared to the baseline assessments. For all patients, the radiation oncologist should perform the baseline physical evaluation 3-10 weeks after the patient's exchange surgery.

Baker Scoring System (See Appendix 1)

All patients will be assigned a Baker Classification score at baseline and at each follow-up interval by the radiation oncologist and plastic surgeon. The Baker score is a standardized 4-point scale, which integrates the texture and appearance of the breast. Grade I is a normal-appearing, soft breast (a Grade IA breast cannot be detected as an implant, while the implant of a Grade IB breast can be detected by physical examination or inspection); Grade II refers to breast implants that are firm but

appear normal; Grade III includes implants that are firm and appear abnormal; Grade IV capsular contracture is the most severe and includes breasts that are hard, painful, and appear abnormal often with severe distortion [46].

Breast MRI

Longitudinal MR studies will be evaluated for capsular contracture.

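### Section 14.1.2 labels Baker grade I as moderate contracture and grades II–IV as severe, so the two labelled rates do not give the moderate-to-severe incidence set as the first secondary objective

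*Combined protocol and SAP*

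**What the plan says.** The first item under Section 2.2 is: "To quantify the incidence of moderate to severe capsular contracture". Section 14.1.2 is the only supplied text that turns this into a statistic. It says that the "incidence of moderate and severe capsular contracture will be examined using proportions of patients who developed Baker grade <II and" ≥II, at the two follow-up times of each group. The word *respectively* ties moderate to <II and severe to ≥II.

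Section 9.3.1 describes the four-grade scale. For the lowest grade: "Grade I is a normal-appearing, soft breast", with a subdivision in which "a Grade IA breast cannot be detected as an implant, while the implant of a Grade IB breast can be detected by physical examination". Next, "Grade II refers to breast implants that are firm but" normal in appearance. Grade III is firm and abnormal in appearance, and grade IV is the most severe. The section sets no threshold for moderate or severe. It refers to Appendix 1, which Section 20.0 lists but whose text was not supplied.

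Two further statements in Section 9.3.1 bear on the analysis: "All follow-up assessments will be compared to the baseline assessments", and "All patients will be assigned a Baker Classification score at baseline and at each follow-up interval by the radiation oncologist and plastic surgeon". Section 16.1 gives these two assessors separate forms (3a and 3b).

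Section 14.1.2 uses the <II versus ≥II cut again for the 12-month MRI comparison in Group 1. It states no cut for the 18-month comparison in Group 2, or for MRI sensitivity and specificity with the Baker score as gold standard.

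**The concern.** A patient with the best grade on the scale is counted as having moderate contracture, and a patient whose implant is firm but looks normal is counted as severe along with grades III and IV. An analyst who follows the sentence literally would publish a moderate rate made up entirely of normal breasts. One who sees the problem would have to choose another threshold, possibly after seeing the data. Either way, the first secondary objective has no usable definition fixed in advance. The same cut also enters the MRI analysis.

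**Working it through.** The plan states no expected contracture rate, so there is no figure to reproduce. The check maps the grades in Section 9.3.1 onto the categories in Section 14.1.2.

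**Step 1, the mapping.** <II = {I}, as IA or IB. ≥II = {II, III, IV}.

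**Step 2, *developed* read as the grade held at the visit, one score per patient.** P(<II) + P(≥II) = 1 for any distribution of grades. Of the 4 × 4 = 16 possible baseline/follow-up pairs, 4 end at grade I and 12 end at II or above; 4 + 12 = 16, so every pair falls in a category. Moderate plus severe is 100% of scored patients whatever happens.

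**Step 3, *developed* read as worsening since baseline.** The worsening pairs are I–II, I–III, I–IV, II–III, II–IV and III–IV: 6 of 16. None ends below grade II, so moderate would be empty apart from a change from IA to IB. All 6 end at ≥II, and one of them (I–II) ends at grade II. These counts show what is possible; they say nothing about rates.

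**Step 4, the ≥II proportion taken alone.** Write g = P(II) and s = P(III) + P(IV). Then P(≥II) = g + s.
- If moderate-to-severe means III–IV, the target is s and the excess is (g + s) − s = g.
- If grade II is the first moderate grade, the target is g + s and the excess is 0.

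The documents give neither g nor s. Three assumed distributions, for illustration only:

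| Assumed I/II/III/IV (%) | Labelled moderate (<II) | Labelled severe (≥II) | III–IV rate | Excess if III–IV is meant | Excess if II is moderate |
|---|---|---|---|---|---|
| 70/20/8/2 | 70 | 30 | 10 | 20 points | 0 |
| 50/30/15/5 | 50 | 50 | 20 | 30 points | 0 |
| 30/40/20/10 | 30 | 70 | 30 | 40 points | 0 |

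In the first row, the distribution with the fewest contractures has the highest labelled moderate rate.

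**Step 5, what the documents say about the threshold.** Section 3.0 uses grades III or IV for significant contracture. The MRI study it describes contrasts I–II (mean capsule 1.14 mm) with III–IV (2.62 mm). Both separate III–IV from the lower grades, but neither uses the words moderate or severe. No supplied text calls grade II moderate.

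**The case against.** The strongest reply is that ≥II on its own may be the intended moderate-to-severe rate, with <II as its complement, so that only the labels and *respectively* are wrong. Grade II is firm, so this is a coherent reading, and the documents do not rule it out. They do not support it either: Section 14.1.2 calls that category severe, and Section 3.0 groups grade II with the lower grades. A reader might therefore infer that the ≥II rate is certainly inflated, or attach a multiplier to it. That goes too far. It treats III–IV as the endpoint, which no supplied text says in those terms, and it needs grade shares that the documents do not give.

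A reader might also infer that the MRI analysis is invalid because its cut differs from that of the cited MRI study. That does not follow. The cited study was cross-sectional, had 22 patients, and not all had been irradiated; nothing obliges the trial to copy its split. MRI is optional, and Section 12.0 describes the quantification of post-radiation changes as descriptive. With all four grades recorded, the other split remains available. What stands is that the cut should be stated once and used throughout.

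An error in reading a symbol from the PDF cannot be fully excluded, but the same cut appears twice in Section 14.1.2. Reading ≤II for <II would put grade II in both categories. Appendix 1 may define the terms, but it could not make grade I moderate without contradicting Section 9.3.1.

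**Conclusion.** The mapping is wrong as written and should be fixed. Grade I cannot be moderate contracture on the protocol's own scale, neither reading of *developed* repairs this, and the two labelled rates together cannot give the incidence in Section 2.2. Whether the ≥II rate alone is also wrong is undetermined: the excess is the grade II share if III–IV is meant, and zero if grade II is meant as moderate.

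The 100% sum assumes one score per patient, whereas the plan collects two and does not say which is used. The effect is limited to secondary reporting. It would be wrong to infer any consequence for the implant-failure endpoint, the sample size or the decision rule, since none of them uses the Baker grade.

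**What to change.** In Section 14.1.2:
- Delete the mapping of moderate to <II and severe to ≥II. State one explicit grade definition of moderate-to-severe contracture that excludes grade I. The default best supported by Section 3.0 is III–IV versus I–II, for the sponsor to confirm against Appendix 1.
- Report the counts of all four grades at each time point, so that either threshold can be read off.
- Apply the same stated cut to the MRI rank-sum and the sensitivity and specificity analyses in both groups.
- Say whether *developed* means the grade held at the visit or worsening since baseline.
- Say whose score is used, the radiation oncologist's or the plastic surgeon's, and how disagreement is handled.

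The cost is wording only. Grades are already assigned at baseline and at each follow-up, so no new data are needed.

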2.0 OBJECTIVES AND SCIENTIFIC AIMS

2.1 Primary Objective

To evaluate the efficacy of multi-beam IMRT in decreasing the rate of implant failure in breast cancer patients who have undergone two-stage expander/implant reconstruction and require PMRT. Implant failure is defined as a surgery requiring removal or replacement of the prosthesis with another type of reconstruction.

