3.0 BACKGROUND AND RATIONALE

Enhancement of survival and preservation of quality of life represent two paramount goals in the treatment of breast cancer. The results of a large meta-analysis established the critical role of PMRT therapy plays in improving disease-free survival in locally advanced breast cancer patients [1]. At the same time, breast reconstruction offers psychosocial and cosmetic benefits to patients who undergo mastectomy and is considered an important component of treatment [2]. In spite of the individual merits of PMRT and reconstruction, the optimal integration of the two modalities has been controversial. Radiation is an independent risk factor for complications in patients with implant reconstructions, including a 2-3-fold increase in the risk of significant capsular contracture (Baker grade III or IV), increased rates of reconstructive failure (3-5 fold increase), decreased satisfaction, and decreased cosmetic outcomes [3,4].

Capsular contracture, in particular, is problematic in patients with implant reconstructions who have received radiation, often leading to pain, discomfort and reconstructive failure. After reconstructive surgery which involves the positioning of an implant under the chest wall, capsules of tightly woven collagen fibers commonly form around the implant [5]. In some patients, the interaction between inflammatory cells, extracellular matrix, and fibroblasts leads to an abnormal response, causing thickening and tightness of the capsule and hence, capsular contracture [6,7]. Factors such as radiation, subclinical infections, hematoma or the absence antibiotics during surgery have been proposed as etiologies of capsular contracture, but the contributions of each of these factors to the

development of capsular contracture is unknown [8-10]. Several studies of pharmacologic intervention for capsular contracture have been published, but lacked the evidence to be used as a true therapeutic measure [11,12]. When severe, capsular contracture can compromise the aesthetic outcome and require surgical intervention such as an open capsulotomy, capsulectomy or removal or replacement of the implant.

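### Contracture incidence rests on Baker grades at scheduled visits, with no rule for contracture corrected by surgery that keeps the implant, so corrections between visits go uncounted

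*Combined protocol and SAP*

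**What the plan says.** The first secondary objective in Section 2.2 is "To quantify the incidence of moderate to severe capsular contracture". Section 14.1.2 puts this into practice as follows: "the incidence of moderate and severe capsular contracture will be examined using proportions of patients who developed Baker grade" below II and II or above, "at 12 or 18 months and 24 or 30 months after IMRT was administered". The proportions are then compared between Groups 1 and 2.

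Section 9.3.1 fixes when grades exist: "All patients will be assigned a Baker Classification score at baseline and at each follow-up interval by the radiation oncologist and plastic surgeon". The visits are at 12 and 24 months after IMRT in Group 1 (Section 10.1) and at 18 and 30 months in Group 2 (Section 10.2). The denominator is broad: "All patients enrolled will be used for the analysis of secondary objectives if they provided eligible measurements". Eligible is not defined, and corrective surgery is not named as a reason for exclusion.

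Section 3.0 foresees that severe contracture can "require surgical intervention such as an open capsulotomy, capsulectomy or removal or replacement of the implant". Capsulotomy and capsulectomy are thus listed apart from removal or replacement. The primary endpoint does not pick them up when the implant is kept: "Implant failure is defined as a surgery requiring removal or replacement of the prosthesis with another type of reconstruction" (Section 2.1). Revisions have their own line in Section 14.1.2, "Incidence of minor revisional surgeries by plastic surgeon will be evaluated by proportions too", with no definition and no link to contracture. Section 12.0 allows ascertainment at any time between the end of IMRT and the end of follow-up, but says so for implant failure only.

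**The concern.** An incidence counts patients who have had the event by a given time. A proportion by grade at a visit counts patients who have the condition on that day. The two differ once the condition can be treated, and the protocol itself says that this one can.

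Two invented Group 1 records show the problem:

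- **Record A:** Grade III at month 12, capsulotomy at month 15, Grade I at month 24.
- **Record B:** Grade IV at month 8, capsulectomy at month 10, Grade I at months 12 and 24.

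Both patients developed significant contracture. Both still have an implant to grade, so both stay in the denominator. Record B is never a case. Record A is a case at 12 months and may or may not be one at 24 months, depending on how the sentence is read.

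At stake is the first secondary objective. The reported rate would be too low, and lower the more contractures are operated on. Under the visit reading, the later figure could fall below the earlier one, which a cumulative incidence cannot do. The comparison of Groups 1 and 2 would mix differences in contracture with differences in surgical practice.

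**Working it through.** **Nothing to reproduce.** For contracture, Section 14.1.2 gives no expected rate, sample size, error rate or decision rule.

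**Step 1: how each record is counted.** The plan allows two readings.

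| Record | Visit prevalence | Cumulative (ever graded by that visit) |
|---|---|---|
| A: graded at the first visit, corrected later | case at 12 months, non-case at 24 | case at both |
| B: arises and is corrected between visits | non-case at both | non-case at both |

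Record B is lost either way, because no grade is planned between visits and surgery is not an event. In each record the non-case status requires a grade below II after correction. A breast left at Grade II still counts under the cut-off of Section 14.1.2.

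**Step 2: room for Record B.** In Group 2 the baseline comes about 6 to 8 months after IMRT (Section 8.0) and the next grade at 18 months, a gap of 18 − 8 = 10 to 18 − 6 = 12 months. The following gap is 30 − 18 = 12 months. In Group 1 the baseline is taken shortly before or during IMRT, so the gap to the first follow-up grade is about 12 months, and the next is 24 − 12 = 12 months. Section 12.0 puts about 92% of contractures within 12 months of surgery, so onset before the first follow-up grade is plausible.

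**Step 3: size under visit prevalence.** Inputs:

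- cumulative incidence c = 30% (assumed; not in the documents);
- early share 92% (Section 12.0, there counted from surgery and used here as onset before the first follow-up visit);
- share s of early cases corrected with the implant kept before the last visit, 10% to 40% (assumed);
- every corrected breast grades below the cut-off (assumed).

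Last-visit proportion = 0.30 × 0.92 × (1 − s) + 0.30 × 0.08 = 0.276 × (1 − s) + 0.024.

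| s | Reported | Relative understatement | Not counted per 100 patients |
|---|---|---|---|
| 10% | 27.2% | 9% | 2.8 |
| 20% | 24.5% | 18% | 5.5 |
| 30% | 21.7% | 28% | 8.3 |
| 40% | 19.0% | 37% | 11.0 |

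**Step 4: size under the cumulative reading.** Only Record B is lost. If f is the share of all contractures that arise and are corrected wholly between visits, the reported figure is c × (1 − f). The documents give no value for f. It cannot exceed the share of all contractures that are corrected, so for the same surgical practice the loss is no larger than in Step 3.

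**Step 5: effect on the group comparison.** Take the same assumed true 40% in both groups, with 10% of cases lost in one and 30% in the other. The reported figures are 0.40 × 0.90 = 36% and 0.40 × 0.70 = 28%, a difference of 8 percentage points where none exists.

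**The case against.** The strongest reply is that Section 14.1.2 speaks of patients who *developed* a grade, and calls the result an incidence. Both words fit a cumulative reading at least as well as a visit reading. A reader might infer that the plan prescribes point prevalence and so loses every corrected patient; the documents do not support that. Record A may well remain a case at 24 months, and in any event she is reported as a case at 12 months. This stands. It does not help Record B.

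Second, Group 2 is planned as two thirds of the patients and has its graded baseline after exchange, so some early contractures would be seen then. This stands too, and it narrows the loss in that group. The gap of 10 to 12 months that follows remains.

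Third, a reader might infer that corrective surgery would pass for a benefit of IMRT. Within this trial it cannot: no contracture comparison against patients without IMRT is planned, the historical comparison concerns implant failure only, and both groups in the contracture comparison receive IMRT.

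Fourth, the illustration is soft. The 30% and the correction shares are not in the documents. The 92% is counted from surgery and cited to a text on augmentation mammoplasty. In Group 2, 12 months after exchange is roughly 4 + 12 = 16 to 8 + 12 = 20 months after IMRT. Section 3.0 gives no frequency for capsulotomy or capsulectomy and does not state outright that the implant is kept. All of this limits what can be said about size, though not about direction.

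Fifth, revisions are reported separately, so the surgery is not hidden. But that proportion does not carry the reason for surgery and cannot be added back to the contracture rate.

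**Conclusion.** The point holds in a limited form. As written, the plan counts a contracture that arises and is corrected between visits as a non-case under either reading, if the breast then grades below the cut-off. It leaves open whether one graded at 12/18 months and corrected later stays a case at 24/30 months. The bias is downward, and unequal correction rates can distort the comparison of Groups 1 and 2.

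The size cannot be known from the documents. The range of 27% to 19% against an assumed 30% is an upper-end illustration for the last visit under the visit-prevalence reading, with every corrected breast below the cut-off.

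This concerns a secondary endpoint without a decision rule and leaves the primary analysis untouched. It still deserves correction, because following the plan as written can understate the quantity that the objective names, and the repair is cheap.

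**What to change.** In Section 14.1.2, define contracture incidence at 12/18 and 24/30 months as cumulative. A patient is a case from the first visit with the qualifying Baker grade, or from the date of any revision surgery whose recorded indication is contracture, and remains a case thereafter. Report the grade at each visit separately, labelled as prevalence.

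For this to work, the qualifying grade must be clear. Section 14.1.2 splits at below II versus II or above under the labels moderate and severe. Section 9.3.1 describes Grade I as a normal-appearing, soft breast, Section 3.0 treats Grade III or IV as significant contracture, and the objective in Section 2.2 is moderate to severe. These passages must be reconciled.

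The cost is SAP wording plus one data item, the date and indication of each revision. The form list in Section 16.1 names no form for it, although revisions are already an endpoint and part of the clinical evaluation in Section 8.0. The drawback is that the endpoint then depends partly on the surgeon's decision to operate, which is why visit prevalence should be shown alongside. Visits and sample size do not change.

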We expect to accrue 3-4 patients per month. Thus, the trial should be completed within 3 years. Efforts will be made to follow-up every patient for at least 24 months (Group 1) or 30 months (Group 2). Since patients may drop off (for reasons unrelated to toxicity) or be lost to follow-up, we will enroll a total of 130 patients. However, only the first 100 patients (subject to the restriction that at minimum 34 are in group 1 and at minimum 66 are in group 2) who have been followed for at least 24/36 months from IMRT will be analyzed towards the primary objective. Only patients who are irradiated to a tissue expander or permanent implant will be counted in the analysis of the primary objective (i.e. patients in the cardiac substudies who do not receive IMRT to the tissue expander or implant will not be included in the analysis of the primary objective).

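### Minor revisional surgery is analysed as a simple proportion with no horizon, follow-up requirement or censoring rule, so it does not estimate risk at a defined time and its bias depends on an unstated denominator

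*Combined protocol and SAP*

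**What the plan says.** Section 2.2 lists the rate of minor revisional surgeries as a secondary objective. The analysis is one sentence in section 14.1.2: "Incidence of minor revisional surgeries by plastic surgeon will be evaluated by proportions too". The sentence before it gives time points for capsular contracture, "at 12 or 18 months and 24 or 30 months after IMRT was administered", but none is stated for revisions. The next sentence adds: "Again, the rates (proportions) will be compared across the two groups".

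The analysis set is defined later in the same section: "All patients enrolled will be used for the analysis of secondary objectives if they provided eligible measurements". The section then says: "Analyses for secondary objectives will be done separately for the two groups". It does not say what an eligible measurement is when the outcome is a surgical event.

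Section 14.1.1 foresees loss: "Since patients may drop off (for reasons unrelated to toxicity) or be lost to follow-up, we will enroll a total of 130 patients". For the primary endpoint it deals with this by a follow-up condition. Only the first 100 patients "who have been followed for at least 24/36 months from IMRT will be analyzed towards the primary objective" (the 36 there is at odds with the 30 months given elsewhere for Group 2, which is a separate matter). For all other patients, 24 or 30 months of follow-up is an aim and not a condition of analysis.

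Section 8.0 includes revisional surgeries in the baseline clinical evaluation. Sections 10.1 and 10.2 schedule clinical evaluations at 12 and 24 months (Group 1) and 18 and 30 months (Group 2). Section 12.0 says that incidence of revisions will be assessed, without a window or denominator.

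**The concern.** A minor revision can happen at any time after IMRT and is seen only while the patient is followed. A proportion estimates its risk by a given time only if everyone in the denominator was observed to that time, or if the shortfall is handled by censoring. The plan does neither for this endpoint, although it recognises the problem for the primary one.

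The consequences are these:
- The reported rate may be too low, about right or too high, depending on a choice that the plan leaves open and that could be made after the data are seen.
- The groups are compared on windows that differ by six months from the end of IMRT. Even with no dropout and equal hazards, the proportions would differ.
- Implant failure ends the chance of a later minor revision of that implant. On the hypotheses in section 14.1.1 it affects 16% to 26% of patients, so its treatment in the estimate should be stated.

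**Working it through.** The documents state no expected revision rate, dropout rate or precision for this endpoint, so there is no figure of theirs to reproduce.

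**Inputs**
- Enrolled 130, analysed for the primary endpoint 100 (section 14.1.1). The difference is an enrolment allowance. Using it as a dropout share, d = 30/130 = 23.1%, is an assumption.
- True risk p by the group's horizon: assumed 20%, with 10% and 30% as a range.
- Dropout independent of revision (assumed). Unless stated otherwise, revision and dropout times are spread evenly over the period, so a dropout is seen for half of it on average.

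**Expected reported proportion for p = 20%, by counting rule**

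1. All dropouts stay in the denominator. Revisions seen: 0.20 × (100 + 30 × 0.5) = 23. Proportion: 23/130 = 17.7%, a relative error of −11.5%. Constant hazards also give 17.7%. If 80% of revisions fall in the first half of the period, the result is 18.4%.
2. As 1, but all dropout at time zero: 0.20 × 100/130 = 15.4%, or −23.1%.
3. A first follow-up visit is required (visit windows ignored).
   - Group 1, 12 of 24 months: half the dropouts stay (15 of 30), seen for 0.75 of the period. 0.20 × (100 + 15 × 0.75)/115 = 0.20 × 111.25/115 = 19.3%, or −3.3%.
   - Group 2, 18 of 30 months: 40% stay (12 of 30), seen for 0.8. 0.20 × (100 + 12 × 0.8)/112 = 0.20 × 109.6/112 = 19.6%, or −2.1%.
4. Completers only: 0.20 × 100/100 = 20%. There is no bias, but all partial follow-up is discarded.
5. Completers, plus dropouts who had a recorded revision: 23/(100 + 30 × 0.20 × 0.5) = 23/103 = 22.3%, or +11.7%.

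| Rule | p = 10% | p = 20% | p = 30% |
|---|---|---|---|
| 1. All kept, even dropout | 8.8% | 17.7% | 26.5% |
| 2. All kept, dropout at time zero | 7.7% | 15.4% | 23.1% |
| 4. Completers only | 10% | 20% | 30% |
| 5. Dropouts only if revised | 11.3% | 22.3% | 33.0% |

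**Smaller dropout share.** If the 10 unirradiated Group 2B controls are inside the 130, the share is 20/120 = 16.7%. For p = 20%, rule 1 gives 0.20 × 110/120 = 18.3%, rule 2 gives 0.20 × 100/120 = 16.7%, and rule 5 gives 22/102 = 21.6%.

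**Group comparison.** Suppose both groups have the same constant hazard, with 20% risk at 24 months. The 30-month risk is then 1 − 0.80^(30/24) = 24.3%. The two proportions would differ by 4.3 points through observation time alone.

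**Time-to-event estimate.** Under independent dropout, cumulative incidence with censoring at last contact targets the true p at the stated time and uses every patient's observed follow-up.

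**The case against.** The strongest objection is that a reader might infer that the plan counts dropouts as revision-free over all enrolled patients, and so understates the rate. The documents do not say this. Section 14.1.2 limits the set to patients with eligible measurements. Section 8.0 treats revisional surgery as part of the clinical evaluation, and the revision sentence follows directly on proportions at 12/18 and 24/30 months. A natural reading is that a patient lost at month 6 has no eligible follow-up evaluation and leaves the denominator. The error is then about 2% to 3% in relative terms, or zero if the final visit is required. This stands: neither the direction nor the size of the bias is fixed by the text.

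The 30 of 130 is also not a dropout rate. More than 100 patients may complete follow-up, since only the first 100 are analysed for the primary endpoint. Sections 9.2.1 and 13.0 remove some patients for other reasons. This stands too, and the figures above are therefore conditional.

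Implant failure as a competing event does not by itself bias the proportion. With complete follow-up, the crude proportion equals the cumulative incidence with failure and death competing. It matters only that the rule be stated.

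The longer Group 2 window has a reason. The schema notes tie it to exchange some 4 to 8 months after IMRT, so 30 months is about 22 to 26 months after exchange. That explains the visit schedule. It does not tell the analyst which clock the comparison of revision rates uses.

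Finally, sampling error is larger than most of these biases. At 20% it is about ±12 points in Group 1 (1.96 × √(0.16/43)) and ±8 in Group 2 (1.96 × √(0.16/87)), taking one third and two thirds of 130. This limits the importance of the point but is no reason to leave the estimator undefined.

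**Conclusion.** The concern holds in a conditional form. The plan uses a simple proportion for an event that accrues over time, without a horizon, follow-up requirement or censoring rule, while expecting losses and guarding against them only for the primary endpoint. The result does not estimate risk at a defined time.

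For an assumed true 20% and an assumed 30/130 independent dropout, the counting rules open to the analyst give 15.4% to 22.3%. The most favourable readings (visit filter or completers only) give 19.3% to 20%. It would go too far to say that the rate is understated, because that follows only if dropouts are kept as revision-free, and the documents do not say so. Nor do they show that dropout differs between groups. The mixing of 24-month and 30-month windows in the comparison does not depend on dropout.

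This is a secondary estimate with no threshold attached, and the primary decision rule is unaffected. The change is worth making because a better estimator is available at little cost.

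**What to change.** In section 14.1.2, replace the proportion for minor revisional surgery with the following:
- Cumulative incidence of first minor revision from the end of IMRT (Aalen-Johansen), by group, at 24 months for Group 1 and 30 months for Group 2, with 95% confidence intervals.
- Censoring at last contact, with implant failure and death as competing events.
- Any comparison between groups at one common time, for example 24 months, with the time origin stated. If time since exchange is of interest, name that as a separate analysis.
- The crude proportion and the total number of revisions kept as description, so that the objective of quantifying rates is not narrowed to first events. Say who is in the denominator by defining an eligible measurement for revisions.

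The estimate assumes that loss to follow-up is independent of revision, and this should be stated.

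The cost is SAP wording and a standard estimate, with no extra patients. The data forms listed in section 16.1 do not name a field for revision date or last-contact date, so the sponsor should confirm that both are captured and add them if not.
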